Pregnant women attending prenatal care will be screened for anemia with repeat CBC at 24 to 28 weeks gestation per standard of care. If the initial Hgb at this gestational age is less than 10 mg/dL, they will undergo testing for iron-deficiency anemia. Iron-deficiency anemia will be defined as anemia with serum ferritin <30ug. Any pregnant woman diagnosed with iron-deficiency anemia who meets all inclusion criteria and no exclusion criteria will be eligible for the study (**Figure 1**). In addition, patients who present for prenatal care after 28 weeks gestation who meet all inclusion criteria and no exclusion criteria will be eligible for enrollment if they are diagnosed with iron-deficiency anemia prior to 34 weeks.

Randomization and Treatment Groups: Patients meeting all inclusion criteria and no exclusion criteria who sign informed consent will be enrolled and randomly assigned in a 1:1 ratio using a computer-generated randomization sequence to one of two treatment protocols. The two treatment protocols are:

- 1. Oral Iron Supplement- Oral iron supplementation will occur throughout pregnancy with ferrous sulfate at a dose range of 325mg daily to 325mg three times daily. Patients will be instructed to take on an empty stomach or with an acidic beverage like orange juice. Patients will continue oral iron supplementation through delivery, then refer to their treating physician for further postpartum consumption. Patients will be asked to report any side effects of oral iron between 2 4 weeks after randomization. Side effects will also be assessed at delivery along with reported compliance to the oral iron regimen.
- 2. Intravenous Iron- The intravenous iron infusion will occur in the form of 975mg of intravenous iron dextran diluted in 250 or 500mL of 0.9% sodium chloride given as a single dose over 1-2 hours. Prior to starting the treatment dose, participants will receive a test dose of 0.5mL (25mg) of iron dextran and will be monitored by hospital nursing staff for 20-30 minutes (or per local infusion protocol) to ensure there are no transfusion IVIDA.Version [6.2] 09.18.2019

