Maternal blood draw: Serum ferritin	SOC			х	
Cord blood collection & processing (Hgb & ferritin; cord gas and/or lactate if performed as clinical necessity)				Х	
Delivery & neonatal outcomes via chart abstraction					Х

^{*}If ferumoxytol is administered due to shortage of iron dextran, two infusions will occur in the prenatal period as outlined in the randomization section of this document. The post-infusion phone call will occur 48-72 hours after the second infusion.

Data analysis: Analyses will follow the intention to treat principle, in which patients will be analyzed in the group to which they were randomized whether or not they received the assigned treatment. Continuous variables will be compared using the Student's t-test or Mann Whitney t test, as appropriate. Categorical variables will be compared using the t or Fisher's exact test, as appropriate. We will calculate crude and unadjusted risk estimates and differences. We will use multivariable logistic regression to adjust for potential confounders. We will estimate the number needed to treat to prevent occurrence of one primary outcome.

Sample size estimation: Based on institutional data the baseline rate of anemia (Hgb<11mg/dl) on admission to labor and delivery among women on supplemental oral iron is 38.5%. We estimate that 108 patients will provide 80% power to detect a 60% or greater relative difference in anemia (38.5% versus ≤15.4%) with intravenous iron (alpha=0.05, 2-tailed test). We will recruit **120 patients** to account for an anticipated 10% loss to follow-up (**Table 1**).

The anticipated effect size of 60% is plausible and conservative. A study by Al *et al.*, the only study that reported the outcome of Hgb <11 at the time of delivery, showed an effect size of 88% (4.4% versus 37.8%, RR 0.12, 95% CI 0.03, 0.48).⁴ Based on preliminary data showing that 10 pregnant women received intravenous iron in 6 weeks at the Washington University Medical Center, we anticipate that the 124 patients will be recruited within 15 months.

Table 1: Sample size estimation (Baseline: 38.5%, Power: 80%, alpha 0.05, loss: 10%)				
Risk Estimate RR (%)	Anticipated Rate	N	N+10%	
0.67 (33)	25.8%	418	460	
0.60 (40)	23.1%	276	304	
0.50 (50)	19.3%	168	185	
0.40 (60)	15.4%	108	120	
0.33 (67)	12.7%	82	90	
0.30 (70)	11.6%	74	81	

HUMAN SUBJECTS PROTECTION

Assessment of Risks

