- v. The study team will monitor, document and report to the Institutional Review Board, any adverse events among study participants per the plan detailed below.

Reportable Events

The PI at each site will oversee the safety of the study at his/her site. During the study, the investigator or study site personnel will be responsible for querying and recording adverse events (AEs) and serious adverse events (SAEs), as detailed below.

Types of Reportable Events:

Serious Adverse Events (SAE)

The site must report all SAEs to the lead site, whether or not they result from study participation, within 24 hours of learning of the event. A serious adverse event (SAE) is any adverse event occurring within the timelines specified in the protocol that results in any of the following outcomes:

- Death
- Life-threatening situation (subject is at immediate risk of death)
- Inpatient hospitalization or prolongation of existing hospitalization
- Persistent or significant disability/incapacity
- Congenital anomaly/birth defect in the offspring of a subject who received study drug
- Important medical events that may not result in death, be immediately life-threatening, or require hospitalization, may be considered an SAE when, based upon appropriate medical judgment, they may jeopardize the subject and may require medical or surgical intervention to prevent one of the outcomes listed in this definition.

Adverse Events (AE)

An adverse event is any untoward medical occurrence in a clinical investigation subject administered an investigational product and which does not necessarily have to have a causal relationship with this treatment. An AE can, therefore, be any unfavorable and unintended sign (that could include a clinically significant abnormal laboratory finding), symptom, or disease temporally associated with the use of a medicinal product, whether or not considered related to the medicinal product.

For this study, abnormal laboratory findings (e.g., clinical chemistry, hematology) or other abnormal assessments (e.g., electrocardiogram, X-rays, vital signs) per se are not reported as AEs. Only the Adverse Events of Special Interest (AESI) defined below will be recorded on the CRFs and in the subject's chart.

Adverse Events of Special Interest (AESI)

Adverse events of particular clinical importance (other than SAEs mentioned above) will be classified as adverse events of special interest (AESIs). For this study, AESIs refer to:

• Mild/moderate reactions:

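### No stratification by gestational age at entry is described for allocation or the primary test; stratifying both is a cheap change with a modest gain if entry week predicts anemia at delivery

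*Combined protocol and SAP*

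**What the plan says.** The section on randomization and treatment groups has women "enrolled and randomly assigned in a 1:1 ratio using a computer-generated randomization sequence to one of two treatment protocols". The Synopsis describes allocation the same way. Neither place mentions strata, blocks or minimization.

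The inclusion criteria admit women from 24 to 34 weeks. There are two routes in. One is the routine blood count at 24 to 28 weeks. For the other, the Screening section adds that "patients who present for prenatal care after 28 weeks gestation who meet all inclusion criteria and no exclusion criteria will be eligible for enrollment" if iron-deficiency anemia is diagnosed before 34 weeks. The Synopsis aims to give the infusion close to 24 weeks, so the plan itself treats timing as relevant.

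The primary outcome is read once, at admission for delivery. The Data analysis paragraph lists two-group tests for categorical variables, crude risk estimates and differences, and a number needed to treat (NNT). It adds: "We will use multivariable logistic regression to adjust for potential confounders". It does not name the covariates, and it does not say whether the crude or the adjusted result is primary.

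The Reportable Events section implies several sites ("The PI at each site will oversee the safety of the study at his/her site"), but their number is not given.

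**The concern.** Two women who deliver at the same gestation can differ by up to ten weeks (34 minus 24) in the time between entry and the admission hemoglobin. If that time affects hemoglobin, gestational age at entry is a prognostic factor. It is known for every woman before randomization, because eligibility depends on it.

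Two things are at stake. In a trial of 120, chance can leave one arm with more late entrants, which weakens the credibility of the crude difference and of the NNT taken from it. And an unstratified test gives up some precision in a trial planned at only 80% power. The logistic regression could recover this, but with covariates and status left open in an open-label trial, the adjusted result can depend on choices made after the data are seen.

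**Working it through.** **Inputs from the protocol.** Anemia 38.5% on oral iron and 15.4% on IV iron, a risk ratio (RR) of 0.40 and a difference of 23.1 points; "alpha=0.05, 2-tailed test"; 108 analyzed (54 per arm), 120 recruited. The stated claim is that "108 patients will provide 80% power to detect a 60% or greater relative difference in anemia".

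**Inputs not in the documents (assumed).** Share entering at 28 weeks or later: 10 to 50%. Late-minus-early gap in the oral-arm anemia rate: 0 to 40 points. RR 0.40 in both strata, with the overall oral-arm rate held at 38.5%. I take the unstratified test to be Pearson's chi-square.

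**1. The plan's own figure.** Unpooled two-proportion formula, n per arm = (1.960 + 0.842)² × [p1(1−p1) + p2(1−p2)] / (p1−p2)²:

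- p1(1−p1) + p2(1−p2) = 0.385×0.615 + 0.154×0.846 = 0.2368 + 0.1303 = 0.3671
- (p1−p2)² = 0.231² = 0.05336
- n = 7.849 × 0.3671 / 0.05336 = 53.99, so 54 per arm and 108 in total; 108/0.90 = 120.

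The stated size is reproduced. The pooled-variance form gives 114, which is why simulated chi-square power at 108 falls slightly below 80%.

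**2. Chance imbalance in late entrants.** Unrestricted 1:1 allocation of 120, simulated. Chance that the arms differ by 10 points or more:

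| Late share | Chance |
|---|---|
| 10% | 7% |
| 20% | 18% |
| 30% | 24% |
| 40% | 27% |
| 50% | 28% |

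If arm sizes were fixed at 60:60, the figures at 10, 30 and 50% would be 9.3, 27.3 and 31.5%, because a difference of exactly six women then counts as 10 points.

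**3. What a 10-point imbalance does to the crude difference.** Put the oral arm 5 points above the mean late share and the IV arm 5 points below. The IV-arm gap is 0.40 times the oral-arm gap.

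- Oral-arm gap 25, IV-arm gap 10: 0.05×25 + 0.05×10 = 1.75 points
- Oral-arm gap 40, IV-arm gap 16: 0.05×40 + 0.05×16 = 2.8 points

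The planned difference is 23.1 points and its standard error at 54 per arm is √(0.3671/54) = 8.2 points. The shift is therefore a fifth to a third of one standard error (1.75/8.2 = 0.21; 2.8/8.2 = 0.34). At the larger shift, the NNT would move from 1/0.231 = 4.3 to between 1/0.259 = 3.9 and 1/0.203 = 4.9.

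**4. Power at 108 analyzed.** Simulated, 2 million trials per setting, two-sided 0.05, CMH without continuity correction:

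| Late share | Oral-arm gap | Simple allocation, chi-square | Simple allocation, CMH | Stratified allocation, CMH |
|---|---|---|---|---|
| 30% | 0 | 78.6% | 78.0% | 78.7% |
| 30% | 10 | 78.6% | 78.1% | 78.9% |
| 30% | 25 | 78.6% | 79.3% | 80.1% |
| 30% | 40 | 78.6% | 81.4% | 82.3% |
| 50% | 0 | 78.6% | 78.0% | 78.7% |
| 50% | 10 | 78.6% | 78.2% | 79.0% |
| 50% | 25 | 78.6% | 79.6% | 80.3% |
| 50% | 40 | 78.6% | 82.3% | 83.0% |

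A gap of 25 to 40 points is a strong effect. At a 30% late share and a gap of 25, the early and late oral-arm rates are 31% and 56%, an odds ratio of (0.56/0.44)/(0.31/0.69) = 2.8. At a 50% share and a gap of 40, they are 18.5% and 58.5%, an odds ratio of 6.2.

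**The case against.** The strongest reply is that the premise is not in the documents. They give no late share and no effect of entry week. Prior oral iron is not excluded, so gestational age at entry need not mark the start of iron treatment. Baseline hemoglobin and ferritin are also known at entry and might predict the outcome better. This stands, and it is why every size above is conditional.

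Second, a reader might infer that the plan ignores gestational age altogether. The documents do not support that. The planned regression could include it, and silence on blocks and strata does not prove that the list is unrestricted. What can be said is that no stratification is described and the adjustment is not prespecified.

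Third, a reader might infer that an imbalance would bias the result. It would not: chance imbalance under valid randomization is already reflected in the type I error and the confidence interval. The cost is precision and credibility.

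Fourth, the analysis change alone is not free. With little or no effect of entry week, CMH under simple allocation loses about 0.3 to 0.6 point of power.

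The site argument is thin. The number of sites is not given, and the reference to local infusion practice concerns only monitoring after the test dose.

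What survives is that entry week is known for every woman, the plan treats timing as relevant, and neither the described allocation nor the named tests use it.

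**Conclusion.** The point holds as a cheap improvement and is not a flaw that threatens validity. Stratified allocation with a stratified test raises power from about 78.6% to about 80 to 83% if 30 to 50% of women enter late and their oral-arm anemia rate is 25 to 40 points higher. It adds 0.1 to 0.4 point if the gap is 10 points or less.

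It is tempting to say that a quarter of such trials would be visibly unbalanced. That fits a late share near 30%; the range is 7 to 28% for shares of 10 to 50%, and the documents do not say where in it this trial lies. It is equally tempting to say that the plan forgoes a sure gain in power. The gain depends on an entry-week effect that the documents do not give.

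The firmest part needs no assumption: the covariates of the adjusted analysis, and whether it or the crude comparison is primary, should be fixed in advance.

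**What to change.** **Allocation (Synopsis and the section on randomization and treatment groups).** State that the list uses randomly varying permuted blocks, stratified by gestational age at randomization (<28 v ≥28 weeks), and by site if sites are few. Varying the block size matters because the trial is open-label.

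**Analysis (Data analysis).** Make the primary analysis the CMH test without continuity correction, stratified by gestational age at entry (<28 v ≥28 weeks). Report the Mantel-Haenszel risk difference and risk ratio, and derive the NNT from that risk difference. Keep the crude estimate as supportive. Say explicitly that no continuity correction is used: with it, power is only about 71 to 76%. For the logistic regression, name the covariates and label the analysis supportive.

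**If recruitment has begun.** Make only the analysis change, and fix it before outcomes are examined by arm.

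**Cost.** Protocol wording and list set-up, with no added patients, visits or blood draws. Many small sites would make strata sparse; then stratify by gestational age only. The analysis-only version risks about 0.3 to 0.6 point of power if entry week has little effect on the outcome.

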Overview: We will conduct an open-label, randomized controlled trial to assess the effectiveness and safety of treating iron-deficiency anemia in pregnant women with intravenous iron compared with oral iron. We test the *hypothesis* that treating iron-deficiency anemia with intravenous iron is associated with improved maternal and neonatal outcomes compared with oral iron. We will use broad inclusion criteria and analyze data using the intention-to-treat principle to increase generalizability of the findings.

Inclusion & exclusion criteria:

Inclusion criteria:

- Pregnant women
- 18 years or older
- Diagnosed with iron-deficiency anemia
 - Serum ferritin <30ug
 - o Hgb <10 g/dl
- Between 24 34 weeks gestation
- Plan to deliver at an in-network hospital
- Able and willing to give informed consent

Exclusion criteria:

- Diagnosis of non-iron-deficiency anemia
- Multiple gestation
- Known or suspected major fetal anomaly or aneuploidy
- Planned delivery at out-of-network hospital
- Unable or unwilling to give consent

Study outcomes:

Primary outcome: The primary outcome of the trial is maternal anemia, defined as Hgb <11mg/dl, on admission for labor and delivery.

Secondary outcomes:

- 1. Safety:
 - i. Mild/moderate infusion reactions: chest tightness, itching, urticaria, flushing, nausea/vomiting, arthralgia, back or joint aches, mild shortness of breath, tachycardia, hypertension or hypotension, abdominal pain, diarrhea, peripheral edema, headache, dizziness, syncope, or numbness.
 - ii. Major infusion reaction: anaphylaxis-like reaction, seizures, or non-reassuring fetal heart rate tracing.

2. Maternal outcomes:

- i. Hgb at admission to labor and delivery
- ii. Hgb on postpartum day 1
- iii. Ferritin at admission to labor and delivery
- iv. blood transfusion
- v. mode of delivery
- vi. postpartum disposition
- vii. readmission

3. Neonatal outcomes

- i. gestational age at delivery
- ii. birth weight
- iii. cord gases (if performed as SOC)
- iv. umbilical artery lactate (if performed as SOC)
- v. APGAR scores
- vi. Hgb (obtained from cord blood)
- vii. Ferritin (obtained from cord blood)
- viii. neonatal morbidities
- ix. postpartum disposition

Screening:

[figure not shown]

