reactions. This amounts to a cumulative dose of 1000mg IV iron dextran. If iron dextran is unavailable due to drug shortage, ferumoxytol will be substituted for this treatment group. Subjects will be given an initial 510mg IV dose in 100 ml 0.9% sodium chloride over at least 15 minutes. This dose will be followed by a second dose of the same concentration 3 to 8 days later. All iron infusions will occur on an obstetric unit equipped with continuous monitoring and emergency equipment. Patients will have continuous fetal monitoring throughout and at least 30 minutes after the infusion. Patients will be called by research staff 48 - 72 hours after infusion (second infusion if administering ferumoxytol) to assess for transfusion reactions. Women who receive intravenous iron will not receive further oral iron supplementation during pregnancy. Postpartum iron supplementation will be left to provider discretion.

Figure 1: Study protocol

^{*}If iron dextran is unavailable due to drug shortage, ferumoxytol will be substituted. The initial dose will be 510mg ferumoxytol IV followed by a second dose of 510mg ferumoxytol IV 3 to 8 days later.

STUDY PROCEDURES

Study patients will have hemoglobin drawn at admission to labor and delivery and on postpartum day one. Neonatal hemoglobin and ferritin (and blood gases and/or lactate if performed out of clinical necessity) will be assessed via cord blood. Obstetric and neonatal outcomes will be collected by a trained research nurse. Subjects randomized to the oral iron group will be asked to report compliance with taking oral iron supplements as well as any side effects of taking the oral iron. This self-report will be assessed during their admission to labor and delivery (or via phone up to 2 days after discharge). See **Figure 2** for schedule of events. Pregnancy, labor and delivery management will be per standard obstetric practice.

Figure 2: Schedule of events

Event	Screening & Enrollment 24-34 weeks	Prenatal Period	48-72 hrs after infusion*	Delivery	Postpartum period prior to discharge
Inclusion/Exclusion	Х				
Informed Consent	X				
Demographics	X				
Prenatal history	X				
Randomization to oral iron vs. IV iron	Х	Oral continues Infusion occurs*			
Phone call: AEs/ outcomes of IV iron			Х		
Effects & outcomes of oral iron supplementation (self-report)		X (Once 2-4 weeks after randomization)		х	
Oral iron compliance (self-report)				х	
Maternal blood draw: Hgb	SOC			х	X PPD1

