- venipuncture complications (blood clot or infection)
- o bowel changes (constipation or diarrhea)
- chest tightness
- itching
- o urticaria
- flushing
- o nausea/vomiting
- o abdominal pain
- o peripheral edema
- arthralgia
- o new onset back or joint aches
- o mild shortness of breath
- tachycardia
- o severe hypertension (For infusion group: confined to infusion timeframe only)
- o severe hypotension (For infusion group: confined to infusion timeframe only)
- o neurological changes (syncope, dizziness, headache) (For infusion group: confined to infusion timeframe only)

Major reactions:

- o anaphylaxis-like reaction (For infusion group: confined to infusion timeframe only)
- o seizures (For infusion group: confined to infusion timeframe only)
- o non-reassuring fetal heart rate tracing (For infusion group: confined to infusion timeframe only)

Assessing and Documenting Reportable Events:

Subjects will be evaluated for adverse events in the following manner:

- Routine monitoring by infusion nurses during the IV iron treatment, with data obtained from the subject's EMR by research staff.
- Subjects will be called by research staff 48-72 hours after infusion to assess for transfusion reactions.
- Subjects on oral iron therapy will be monitored via their EMR and via contact with research staff as outlined in schedule of events

An adverse event report will be generated for each event that will include the following:

- Date of event discovery
- Severity (mild, moderate, severe, life threatening/disabling, death)
- Relationship to treatment
- Action taken
- Outcome
- Expected or not
- Date reported
- Relevant notes/chart records/supporting documentation to corroborate the event
- To whom event was reported (i.e. IRB, lead site, etc.)
 - Non- serious AESIs will be reported to the lead site within 5 days of discovery, and to the IRB at renewal.
 - SAEs and SAESIs will be reported within 24 hours of discovery to the IRB and the lead site.

Relationship of Reportable Events:

An investigator must make the determination of relationship to the drug for each SAE and/or AESI. The relationship to the drug should be assessed using the guidelines presented in the table below.

Relationship to Drug	Description
Related	Previously known toxicity of agent; or
	 Follows a reasonable temporal sequence from administration of the drug; or
	• Follows a known or expected response pattern to the suspected intervention; or

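### If ferumoxytol is substituted, delayed reactions to the first infusion have no scheduled enquiry before the second infusion and are first asked about 5 to 11 days later

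*Combined protocol and SAP*

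**What the plan says.** Ferumoxytol replaces iron dextran only in a drug shortage. It is given as two infusions: "This dose will be followed by a second dose of the same concentration 3 to 8 days later" (Randomization and Treatment Groups, Intravenous Iron).

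The same item sets the follow-up call: "Patients will be called by research staff 48 - 72 hours after infusion (second infusion if administering ferumoxytol) to assess for transfusion reactions". The footnote to Figure 2 (Schedule of events) agrees: "The post-infusion phone call will occur 48-72 hours after the second infusion". Figure 2 has a single call row for intravenous iron. Its other symptom-enquiry row applies to the oral arm.

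Two safety sections describe the call without naming the infusion. Assessing and Documenting Reportable Events says "Subjects will be called by research staff 48-72 hours after infusion to assess for transfusion reactions", and item iv of Protections Against Risks is similar.

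Reactions on the unit have their own source: "Routine monitoring by infusion nurses during the IV iron treatment, with data obtained from the subject's EMR by research staff". The Intravenous Iron item adds: "Patients will have continuous fetal monitoring throughout and at least 30 minutes after the infusion".

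Infusion reactions are the first-listed secondary outcome. The mild/moderate group under Study outcomes begins "chest tightness, itching, urticaria, flushing, nausea/vomiting, arthralgia, back or joint aches, mild shortness of breath, tachycardia".

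**The concern.** The call is the only scheduled prospective way to learn of a reaction that starts after an intravenous-arm participant has left the unit. With iron dextran there is one infusion and one call. With ferumoxytol there are two infusions and still one call, placed after the second.

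Two consequences follow for delayed symptoms:

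- Those caused by the first infusion are recalled over a longer interval, so mild and short-lived ones may be missed.
- A participant asked once about two exposures a few days apart may not place a symptom after the right one. The adverse event report fields include the date of discovery but list neither an onset date nor an infusion number. Events from either infusion first mentioned on that call would share a discovery date. The relatedness table nevertheless asks the investigator to weigh the time sequence from administration to event.

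At stake is the completeness of a listed secondary safety outcome, and how well its events can be assigned to an infusion.

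**Working it through.** The protocol states no figure for this interval, so there is none to reproduce. The check is interval arithmetic, plus a reading of what else could capture the same events.

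**Inputs**
- Gap between ferumoxytol infusions: 3 to 8 days (Intravenous Iron item; Figure 1 note).
- Call: 48 to 72 hours, which is 2 to 3 days, after the second infusion (Intravenous Iron item; Figure 2 footnote).
- Iron dextran: one infusion, with the call 2 to 3 days later (same item).

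**Time from exposure to enquiry**
- First ferumoxytol infusion = gap + call delay. Minimum 3 + 2 = 5 days; maximum 8 + 3 = 11 days.
- Second ferumoxytol infusion, or the single iron dextran infusion: 2 to 3 days.
- Excess for the first infusion = the gap itself, 3 to 8 days (5 − 2 = 3; 11 − 3 = 8).

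**Order of events.** The call comes at least 2 days after the second infusion, so no scheduled call precedes it.

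**Which reactions depend on the call.** Events during the infusion are seen by nurses and taken from the medical record. For the infusion group, the list of adverse events of special interest also confines the major reactions, severe hypertension and hypotension, and neurological changes to the infusion period. It sets no such limit on chest tightness, itching, urticaria, flushing, nausea/vomiting, arthralgia or mild shortness of breath. The gap therefore concerns mild or moderate reactions of this kind that begin after the participant leaves the unit.

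**Feasibility of a call after each infusion**
- Recall of the first infusion would fall from 5-11 days to 2-3 days.
- The call window would close on day 3, and the second infusion falls on day 3 at the earliest. Slack is 3 − 3 = 0 days at the shortest gap and 8 − 3 = 5 days at the longest. The call can therefore fall before the second infusion, without margin at the shortest gap.

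**Number of women.** The documents give no shortage probability. With 120 women randomized 1:1, the intravenous arm has 120 / 2 = 60. The number affected could be anything from 0 to 60, which is a bound and not an estimate.

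**The case against.** The case against giving this much weight is substantial, and several stronger readings fail.

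- *A reader might infer that reactions to the first infusion go unrecorded, or that the team has no tolerance information, before re-exposure.* The documents do not support this. Each infusion is monitored on an obstetric unit, and nurse observations reach the study through the medical record. The protocol also does not describe the assessment at the second visit; its silence does not show that nobody asks about symptoms there. Reportable Events gives site personnel a general duty to query adverse events, though it sets no time point.
- *A reader might infer that the sections contradict each other.* They do not. The safety sections give a general rule, and the treatment section and Figure 2 footnote agree on the special case. The general wording is merely less specific. Even so, in a multi-site trial, staff working from the safety section could reasonably call after each infusion, so alignment is worthwhile.
- *A reader might infer that reactions to the two infusions cannot be separated.* This is not shown. On-unit events belong to a known infusion, each event gets its own report, and the eCRF and call script are not among the documents. What can be said is that the listed report fields do not require separation.
- *A reader might infer a biased comparison.* The Data analysis section plans no contrast between the two products, and the primary outcome is untouched. The oral arm is asked 2 to 4 weeks after randomization and again at delivery, so 5 to 11 days is not the longest recall in the trial. That parallel is imperfect, because the oral arm reports on continuing daily treatment and not on one dated infusion.

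These points limit the size of the problem. They leave standing that delayed first-infusion reactions have no scheduled enquiry until after the second infusion.

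**Conclusion.** The point holds within a narrow scope. If ferumoxytol is used and the plan is followed exactly, delayed, out-of-hospital mild or moderate reactions to the first infusion are first asked about 5 to 11 days after exposure, against 2 to 3 days for iron dextran. The same call also covers a second exposure. Under-reporting and uncertain attribution are plausible consequences, but the documents do not allow them to be quantified.

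The conclusion assumes that the specific wording governs over the general wording, and that no unscheduled enquiry fills the gap. It matters only in a shortage of unknown extent. This is a modest weakness in the capture of a secondary safety outcome, worth correcting because the correction is cheap.

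**What to change.** 1. In the Intravenous Iron item and the Figure 2 footnote, schedule a 48-72 hour call after each ferumoxytol infusion.
2. On the eCRF, record the onset date and infusion number for each reaction.
3. Bring item iv of Protections Against Risks and the call entry under Assessing and Documenting Reportable Events into line, so that all four places say the same thing.

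The cost is one extra short call per ferumoxytol participant by research staff who already make these calls (at most 60, if the whole intravenous arm were affected), plus a schedule and eCRF edit. The change concerns ascertainment only; no dosing or clinical rule is proposed.
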